9.1.4 Tumor Tissue Collection and Correlative Studies Blood Sampling

Specific Standard Operating Procedures for sample collection will be used according to our Internal Sample Collections Guidelines following the schedule reported in section 8.0.

Residual sample material available after completion of the designated analyses may be used in the future for identification of additional pharmacodynamic or predictive markers or to enhance understanding of disease biology. If biomarker samples are drawn but study drug(s) is not administered, samples will be retained.

9.1.4.1 Mandatory assays

- Assessment of MMR/MSI status and MGMT expression:** during the screening phase all patients will be tested for the expression of MMR proteins by IHC on the diagnostic FFPE block or slides, or for microsatellite instability by PCR analysis of unstable microsatellite loci (Bethesda panel). All MMR proficient or MSI-low patients, will be assessed for expression of MGMT by IHC on diagnostic FFPE blocks or slides. MGMT-negative cases by IHC will be confirmed by MGMT promoter methylation analysis on tissue. Percent of methylation will be normalized on tumor content

evaluated by hematoxylin and eosin staining to correct for stromal infiltration present in the original slide used for DNA extraction.

- **Mutational Load determination:** the mutational load (ML) will be determined in tissue (TMZ-ML mandatory) and plasma (translational) by NGS on Illumina platform with a minimum depth of 10X and using a proprietary bioinformatic pipeline (IDEA) to estimate the mutational burden normalized per mega base (MB). Only alterations supported by 5% significance level are considered.

ML will be assessed in MGMT-methylated, MMR-Proficient patients enrolled in the TMZ PRIMING Phase in samples collected at different time points, as follows:

- *Baseline Mutational Load (B-ML):* Pre TMZ treatment, in tissue (non-mandatory) and plasma (translational) samples collected before TMZ administration.
- *Priming Mutational Load (TMZ-ML):* at PD post TMZ treatment to declare patients eligible or not for the pembrolizumab TRIAL Phase, in tissue (mandatory) and plasma (translational) samples. NOTE: Patients with a TMZ-ML > 20/mB will be eligible for P- cohort of PEMBRO Trial Phase
- *Dynamic Mutational Load (D-ML):* pre pembrolizumab first dose in either tissue (only D-cohort, whenever possible) or plasma (both cohorts, translational).
- *Progression Mutational Load (PD-ML):* at PD during/after pembrolizumab treatment, in tissue (whenever possible) and plasma (translational) samples.

Timepoints for tissue biopsy and blood sampling are reported in trial diagram (Figure 4.2) and detailed in section 8.0 – Trial Flow Chart.

9.1.4.2 Companion translational assays.

The following samples, in addition to the mandatory tissue sample (see 9.1.4.1), are collected, stored and used to perform complementary translational assays:

- Diagnostic FFPE blocks which are collected for all patients and stored until the end of the trial.
- Peripheral blood samples will be also collected along trial treatments following the schedule reported in section 8.0: in particular every 2 cycles for TMZ and before every treatment for pembrolizumab, from subjects enrolled in both D- and P-cohorts.
- Vital tumor tissue from tumor biopsy which are collected, at baseline (B-ML) and at tumor progression after TMZ treatment (TMZ-ML), before (only Cohort-D) and at tumor progression (both Cohorts) after pembrolizumab treatment when possible (D-ML and PD-ML).

Complementary translational assays may include analysis on:

Serum. To identify potential new serum markers with prognostic and/or predictive value for clinical outcomes (response, progression-free survival and overall survival, toxicity), soluble factors, such as cytokines, chemokines, soluble receptors, and antibodies to tumor antigens will be characterized and quantified by immunoassays in serum. Analyses may include, but not necessarily be limited to: soluble PD-1, Interleukines (1 β , 2, 4, 6, 10, 12 α), **Tumor Necrosis Factor (TNF)**, **TGFbeta**, **Interferon gamma (IFN γ)**, monocyte chemotactic protein (MCP-1), and others;

Peripheral Blood Mononuclear Cells (PBMC). To characterize circulating immune cells specific lymphocyte subsets will be isolated from PBMC and expression levels of T cell co-stimulatory markers on PBMC will be quantified by flow cytometry. Analyses may also include, but not necessarily be limited to, the quantification of **T (CD3; CD4; CD8** and the proportion of memory and effector T cell subset), **B, NK (CD3-; CD56+)** and **TREG (CD3+/CD4+; CD25+; FOXP3+)**, **MDSC (CD33+;CD11b, CD14-; HLA-DR low)** cell-subsets, and the evaluation of expression levels of **PD-1, PD-L1**, and others immune-regulatory molecules on the same subsets of cells. To identify potential neo-antigens, T cell receptor (TCR) re-arrangements will be analyzed by NGS analysis of PBMC or subsets of Lymphocytes isolated by FACS. Amplification and sequencing of CDR3 regions in rearranged TCR β -chains will be analyzed using the immunoSEQ Assay (Adaptive Biotechnologies). The assay combines multiplex PCR with high-throughput sequencing and a sophisticated bioinformatics pipeline for TCR β CDR3 region analysis.

To identify potential predictive signature(s) of response to pembrolizumab gene expression profiling will be determined from PBMC or circulating immune cell-subsets isolated by FACS by RNASeq and/or Affymetrix gene array technology and/or quantitative real-time polymerase chain reaction (qPCR).

Tumor Samples. Biopsy samples may be used for the following analysis:

Characterization of tumor infiltrating lymphocytes (TILs) and tumor antigens. Immunohistochemistry (IHC) will be used to assess the number and composition of immune infiltrates in order to define the immune cell subsets present within formalin-fixed, paraffin embedded (FFPE) tumor tissue. These IHC analyses will include, but not necessarily be limited to, the following markers: **CD4, CD8, CD45RO, FOXP3, PD-1, PD-L1, PD-L2, myeloid cell markers (CD33, CD68, CD11b)** and others.

Characterization of T cell repertoire. TCR sequencing (immunoseq) will be performed on tumor biopsies in order to characterize T cell clonality, either on FFPE or RNA later-preserved samples or on subsets of immune cells isolated from fresh tumor tissue.

Gene expression profiling. Tumor biopsies that are collected in RNA later or equivalent fixative or FACS-sorted cell population isolated from fresh tumor biopsies will also be examined for mRNA gene expression by RNASeq and/or Affymetrix gene array technology and/or quantitative real-time polymerase chain reaction (qPCR) to detect expression of genes with possible prognostic or predictive value.

Immune cells isolated from blood (fresh isolated or vitally DMSO-cryopreserved PBMC or immune cell subsets) and biopsies (tumor infiltrating immune cells) might undergo functional assays to assess specific neoantigen recognition and to investigate molecular markers of response.

Biopsies at confirmed progression are strongly encouraged for the purposes of understanding mechanisms of resistance to therapy.

Other translational studies.

Microbiome analysis. The composition of gut microbiome had been correlated with pathogenesis and progression of colorectal cancer through several mechanisms, including induction of chronic inflammation. In addition, the composition of microbiome had been suggested to influence the innate and adaptive immune system composition and function possibly influencing the activity of pembrolizumab in colorectal cancer.

Thus DNA and RNA may be extracted from fecal samples or buccal swabs taken prior to therapy and on-treatment, and microbiota might be isolated from the same samples for functional analysis, with the purpose of characterizing the gut microbiome and to correlate longitudinal changes in its composition with response to therapy. Patients will be provided with the kit and the instructions for the collection of stools, and they will be asked to fill a diary reporting diet information on the 3 days before collection.

The relative priority of each individual assays might change over time depending on the availability of material, and according to the results of the currently prioritized marker analyses.

9.1.5 Laboratory Procedures/Assessments

Details regarding specific laboratory procedures/assessments to be performed in this trial are provided below.

Laboratory tests for hematology, chemistry, urinalysis, and others are specified in Table 9.1.5

Table 9.1.5 Laboratory Tests

Hematology	Chemistry	Urinalysis	Other
Hematocrit	Albumin	Blood	Serum β -human chorionic gonadotropin†
Hemoglobin	Alkaline phosphatase	Glucose	(β -hCG)†
Platelet count	Alanine aminotransferase (ALT)	Protein	PT (INR)
WBC (total and differential)	Aspartate aminotransferase (AST)	Specific gravity	aPTT
Red Blood Cell Count	Lactate dehydrogenase (LDH)	Microscopic exam (If abnormal)	Total triiodothyronine (T3)
Absolute Neutrophil Count	Carbon Dioxide ‡	results are noted	Free tyroxine (T4)
Absolute Lymphocyte Count	(CO₂ or bicarbonate)	Serum pregnancy test †	Thyroid stimulating hormone (TSH)
	Uric Acid		
	Calcium		
	Chloride		Blood for correlative studies
	Glucose		Stools
	Phosphorus		Buccal Swab
	Potassium		
	Sodium		
	Magnesium		
	Total Bilirubin		
	Direct Bilirubin (If total bilirubin is elevated above the upper limit of normal)		
	Total protein		
	Blood Urea Nitrogen		
	Creatinine/Creatinine Clearance		
† Perform on women of childbearing potential only.			
‡ If considered standard of care in your region.			

Laboratory tests for screening or entry into the Second Course Phase should be performed within 10 days prior to the first dose of treatment. After Cycle 1, pre-dose laboratory procedures can be conducted up to 72 hours prior to dosing. Results must be reviewed by the investigator or qualified designee and found to be acceptable prior to each dose of trial treatment.

9.1.6 Other Procedures

9.1.6.1 Withdrawal/Discontinuation

When a participant discontinues/withdraws prior to trial completion, all applicable activities scheduled for the final trial visit should be performed at the time of discontinuation. Any adverse events which are present at the time of discontinuation/withdrawal should be followed in accordance with the safety requirements outlined in section 9.2 - Assessing and Recording Adverse Events. Participants who a) attain a CR or b) complete 24 months of treatment with pembrolizumab may discontinue treatment with the option of restarting treatment if they meet the criteria specified in section 7.3.5. After discontinuing treatment following assessment of CR, these participants should return to the site for a Safety Follow-up Visit (described in section 9.1.7.4.1) and then proceed to the Follow-Up Period of the study (described in section 9.1.7.4.2).

9.1.6.2 Blinding/Unblinding

This is an open-label trial; therefore, the Sponsor, investigator and subject will know the treatment administered.

9.1.7 Visit Requirements

Visit requirements are outlined in section 8.0 - Trial Flow Chart. Specific procedure-related details are provided above in section 9.1 - Trial Procedures.

9.1.7.1 Screening Phase period

CT scans performed up to 28 days prior to screening eligibility check are considered valid. From -28 to -1 days before the TMZ priming baseline visit as reported in section 8.0 - Trial Flow Chart.

All patients at the baseline of the Screening Phase will be tested for MMR status on the diagnostic FFPE block or slides according to the IHC MSI test (Bethesda panel).

All MMR proficient patients, will be assessed for immunohistochemical expression of MGMT as previously described (9.1.4.1). IHC negative cases will be assessed for MGMT promoter methylation status on tissue as described previously (9.1.4.1). Percent of methylation will be normalized on tumor content evaluated by hematoxylin and eosin staining to correct for stromal infiltration present in the original slide used for DNA extraction. Tumors with values below 63% will be considered MB-low, while those with values above or equal to 63% will be considered MB-high.

9.1.7.2 PRIMING Phase Period

Each patient will be treated until PD unless patient refusal, consent withdrawal, or the occurrence of unacceptable toxicity.

The treatment period (cycle) comprises 28 days, consisting of 5 days of daily administration, followed by a 23-day resting period, from Day 6 to Day 28. During each treatment cycle, extension of treatment period to Days > 5 is not allowed, even in case of missed doses. A diary of TMZ assumption must be given to the patient every treatment cycle and the correct compilation must be revised by the investigator.

9.1.7.3 TRIAL Phase Period

Patients eligible for the TRIAL phase will be treated with Pembrolizumab. The drug will be administered every 3 weeks unless earlier progression, patient refusal, consent withdrawal, or the occurrence of unacceptable toxicity (see section 7.3).

The treatment period (cycle) comprises 21 days, consisting of 1 day of daily administration, followed by a 20-day resting period, from Day 2 to Day 21.

9.1.7.4 Post-Treatment TRIAL Phase Visits

Patients who discontinue Pembrolizumab treatment should be scheduled for a safety follow-up visit within 30 days after the last dose of study or after the decision to discontinue study treatment.

9.1.7.4.1 Safety Follow-Up TRIAL Phase Visit

The mandatory Safety Follow-Up Visit should be conducted approximately 30 days after the last dose of study treatment or before the initiation of a new anti-cancer treatment, whichever comes first. All AEs that occur prior to the Safety Follow-Up Visit should be recorded. Participants with an AE of Grade > 1 will be followed until the resolution of the AE to Grade 0-1 or until the beginning of a new anti-cancer therapy, whichever occurs first. SAEs that occur within 90 days of the end of treatment or before initiation of a new anti-cancer treatment should also be followed and recorded. Participants who are eligible for retreatment with pembrolizumab (as described in 7.3.5) may have up to two safety follow-up visits, one after the Initial Treatment Period and one after the Second Course Treatment.

9.1.7.4.2 Follow-up Visits

Participants who discontinue study treatment for a reason other than disease progression will move into the Follow-Up Phase and should be assessed every 8 weeks (56 ± 7 days) by radiologic imaging to monitor disease status. After 1 year, the imaging time point will occur every 12 weeks (± 7 days). Every effort should be made to collect information regarding disease status until the start of new anti-cancer therapy, disease progression, death, end of the study or if the participant begins retreatment with pembrolizumab as detailed in section 7.3.5.

Information regarding post-study anti-cancer treatment will be collected if new treatment is initiated.

Participants who are eligible to receive retreatment with pembrolizumab according to the criteria in section 7.3.5 will move from the follow-up phase to the Second Course Phase when they experience disease progression.

9.1.7.4.3 Survival Follow-up

Participants who experience confirmed disease progression or start a new anticancer therapy, will move into the Survival Follow-Up Phase and should be contacted by telephone every 12 weeks to assess for survival status until death, withdrawal of consent, or the end of the trial, whichever occurs first.

9.2 Safety Assessment

All patients will be evaluable for safety and toxicity from the time of their first treatment with temozolomide and pembrolizumab. Toxicity will be assessed using NCI Clinical Trials Criteria for Adverse Events (CTCAE) Version 4.03 (see appendix 2). All adverse events (AEs) occurring after the last administration of study treatment will be recorded on the case report forms (CRF) as described below (section 9.2.6). The investigator will decide if those events are drug related (not related, not likely, possibly, probably, certainly) and this decision will be recorded on the forms for all AEs. Serious adverse events (SAEs), as defined by the GCP Guideline, must be immediately reported according to the procedure detailed below (section 9.2.1).

9.2.1 Definitions for Adverse Event and Serious Adverse Event

An Adverse Event (AE) is defined as any untoward medical occurrence in a patient or clinical investigation participant administered a medicinal product and which does not necessarily have to have a causal relationship with this treatment. An AE can therefore be any unfavourable and unintended sign (including an abnormal laboratory finding, for example), symptom, or disease temporally associated with the use of a medicinal product or protocol-specified procedure, whether or not considered related to the medicinal product or protocol-specified procedure. Any worsening (i.e., any clinically significant adverse change in frequency and/or intensity) of a pre-existing condition that is temporally associated with the use of the investigational products, is also an AE.

AEs may occur during the course of the use of investigational product in clinical trials, or as prescribed in clinical practice, from overdose (whether accidental or intentional), from abuse and from withdrawal.

A Serious Adverse Event (SAE) is any adverse event that:

- Results in death;
- Is life threatening;
- Results in persistent or significant disability/incapacity;

- Results in or prolongs an existing inpatient hospitalization;
- Is a congenital anomaly/birth defect;
- Is another important medical event
- **Note:** In addition to the above criteria, adverse events meeting either of the below criteria, although not serious per ICH definition, are reportable to the delegated pharmacovigilance service and to Merck Global Safety (if concerning pembrolizumab, Attn: Worldwide Product Safety; [contact]) in the same timeframe as SAEs to meet certain local requirements. Therefore, these events are considered serious by Merck for collection purposes.
- Is a new cancer (that is not a condition of the study);
- Is associated with an overdose.

Refer to Table 9.2 for additional details regarding each of the above criteria.

9.2.2 Reporting of Adverse Events

AEs will be collected from the time the first dose of study medication (either pembrolizumab or temozolomide) is administered until 30 days following discontinuation of study treatment. SAEs will be collected over the same time period as stated above for AEs of temozolomide, or up to 90 days for pembrolizumab. In addition, any SAE assessed as related to study participation, study medication or concomitant medication must be recorded from the time a subject consents to participate in the study up to and including any follow-up contact. After discontinuation of study medication, the investigator will monitor all AEs/SAEs that are ongoing until resolution or stabilization of the event or until the subject is lost to follow-up.

Reporting criteria for AEs/SAEs:

- All AEs, SAEs and other reportable safety events that occur after the consent form is signed but before planned treatment initiation must be reported by the investigator if the event cause the participant to be excluded from the study.
- All AEs must be reported by the investigator from the time of treatment allocation through 30 days following cessation of study treatment.
- SAEs regarding pembrolizumab must be reported by the investigator from the time of treatment allocation through 90 days (pembrolizumab) or 30 days (temozolomide) following cessation of study treatment, or 30 days following cessation of study treatment if the participant initiates new anticancer therapy, whichever is earlier.
- All pregnancies must be reported by the investigator from the time of treatment allocation through 120 days (pembrolizumab) or 90 days (temozolomide) following cessation of study treatment, or 30 days following cessation of study treatment if the participant initiates new anticancer therapy, whichever is earlier.

- Any SAE brought to the attention of an investigator at any time outside of the time period specified above must be reported immediately by the investigator if the event is considered to be study drug-related.
- A death on study requires reporting regardless of causality and attribution to treatment or other cause must be provided. Death due to disease progression is not to be reported as an AE. Deaths that occur beyond 30 days after the end of study drug administration/initiation of an alternate therapy, do not qualify as SAEs.

Note: Adverse events will not be collected for subjects during the SCREENING Phase period (for determination of archival tissue status) as long as that subject has not undergone any protocol-specified procedure or intervention. Since we will use FFPE blocks and routine blood draws to determine both MMR and MGMT status the subject will first required to provide consent to the main study but AEs will NOT be captured.

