7.3.2 Timing of Dose Administration

Trial treatment should be administered on Day 1 of each cycle after all procedures/assessments have been completed as detailed on the Trial Flow Chart (section 6.0).

- Pembrolizumab 200 mg will be administered on an outpatient basis as a 30 minute IV infusion every 3 weeks. Sites should make every effort to target infusion timing to be as close to 30 minutes as possible. However, given the variability of infusion pumps from site to site, a window of -5 minutes and +10 minutes is permitted (i.e., infusion time is 30 minutes: -5 min/+10 min).
- Pembrolizumab may be administered up to 3 days before or after the scheduled Day 1 of each cycle due to administrative reasons.

7.3.2 Dose Modification and toxicity management for immune-related AEs associated with pembrolizumab

AEs associated with pembrolizumab exposure may represent an immunologic etiology. These immune-related AEs (irAEs) may occur shortly after the first dose or several months after the last dose of pembrolizumab treatment and may affect more than one body system simultaneously. Therefore, early recognition and initiation of treatment is critical to reduce complications.

- Based on existing clinical study data, most irAEs are reversible and could be managed with interruptions of pembrolizumab, administration of corticosteroids and/or other supportive care.
- For suspected irAEs, ensure adequate evaluation to confirm etiology or exclude other causes. Additional procedures or tests such as bronchoscopy, endoscopy, skin biopsy may be included as part of the evaluation. Based on the severity of irAEs, withhold or permanently discontinue pembrolizumab and administer corticosteroids.
- Dose modification and toxicity management guidelines for irAEs associated with pembrolizumab are provided in Table 7.3.2.

Table 7.3.2 Dose modification and toxicity management guidelines for immune-related AEs associated with pembrolizumab

General instructions:				

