8.0 TRIAL FLOW CHART

Trial Period:	SCREENING Phase	PRIMING Phase		TRIAL Phase		End of Treatment	Post-Treatment		
Treatment Cycle/Title:	Baseline Screening Phase (Visit 1)	TMZ Cycle 1 Day 1 and 5	Cycle \geq 2 Day 1 and 5	Pembro Cycle 1 Day 1 Q3	Cycle \geq 2 Day 1 Q3 week	Discontinuation	Safety Follow-up Visit (7)	Follow Up Visits (8)	Survival Follow-Up
Scheduling Window (Days):	Up to 28 days before Start of priming phase	treatment day 1, before drug administration	At time of Discontinuation	30 days post discontinuation	Every 8 weeks post discontinuation	Every 12 weeks			
Administrative Procedures									
SCREENING Phase Informed Consent	X								
PRIMING Phase Informed Consent		X							
TRIAL Phase Informed Consent				X					
Inclusion/Exclusion Criteria	X	X		X					
Demographics and Medical History	X								
Clinical Procedures/Assessments									
Prior and Concomitant Medication Review		X	X	X	X	X	X	X	
Post-study anticancer therapy status							X	X	
Survival Status									X
Treatment Administration (Temozolomide)		X ₁	X ₁						
Treatment Administration (Pembrolizumab)				X	X				
Review Adverse Events		X	X		X	X	X		
Full Physical Examination		X	X	X	X	X	X	X	
Vital Signs, Height and Weight		X	X	X	X	X	X	X	
ECG		X		X					
ECOG Performance Status		X	X	X	X	X	X	X	

Trial Period:	SCREENING Phase	PRIMING Phase		TRIAL Phase		End of Treatment	Post-Treatment		
Treatment Cycle/Title:	Baseline Screening Phase (Visit 1)	TMZ Cycle 1 Day 1 and 5	Cycle ≥ 2 Day 1 and 5	Pembro Cycle 1 Day 1 Q3	Cycle ≥ 2 Day 1 Q3 week	Discontinuation	Safety Follow-up Visit (7)	Follow Up Visits (8)	Survival Follow-Up
Scheduling Window (Days):	Up to 28 days before Start of priming phase	treatment day 1, before drug administration	At time of Discontinuation	30 days post discontinuation	Every 8 weeks post discontinuation	Every 12 weeks			
Laboratory Procedures/Assessments: analysis performed by LOCAL laboratory									
Pregnancy Test – Serum β-HCG		X		X					
PT/INR and aPTT		X	X	X	X	X	X		
CBC with Differential		X	X	X	X	X	X		
Comprehensive Serum Chemistry Panel		X	X	X	X	X	X		
Urinalysis		X							
T3, FT4 and TSH				X	Q6 weeks or when clinically indicated				
Efficacy Measurements									
Tumor Imaging		X	Q8 weeks	X	Q9 weeks	X		X	
Archival Tissue Collection/Tumor Biopsies/Correlative Studies									
Archival Tumor FFPE	X								
Tumor Biopsies (2)		X	at PD ^{3;4}	X		X			
Correlative Studies - Blood Collection		X ⁵	at PD	X	X	X			
Correlative Studies - Faeces Collection		X	at PD	X	X ⁶	X			

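### The flow chart schedules no adverse-event review at pembrolizumab cycle 1 or after the 30-day visit, although serious events are due to day 90, and cohort P has no rule assigning events to temozolomide or pembrolizumab

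*Combined protocol and SAP*

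**What the plan says.** Section 9.2.2 opens AE collection when the first dose of either drug "is administered until 30 days following discontinuation of study treatment". For serious events it adds: "SAEs will be collected over the same time period as stated above for AEs of temozolomide, or up to 90 days for pembrolizumab". Section 9.1.7.4.1 repeats the 90 days for serious adverse events (SAEs), and section 9.2.5 sets the same limit for events of clinical interest (ECIs). The second section numbered 7.3.2 warns that immune-related events "may occur shortly after the first dose or several months after the last dose of pembrolizumab treatment".

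Section 9.1.2.1 refers to the flow chart for the timing of AE assessment and allows more frequent assessment if clinically indicated. In section 8.0 the row "Review Adverse Events" is ticked for both TMZ columns, pembrolizumab cycle 2 onward, discontinuation and the 30-day safety visit. It is empty at pembrolizumab cycle 1, at the follow-up visits and at survival follow-up.

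After the safety visit two kinds of contact remain. Patients who stop without progression are imaged every 8 weeks to follow their disease (9.1.7.4.2). Patients with confirmed progression or new therapy "should be contacted by telephone every 12 weeks to assess for survival status until death" or another end point (9.1.7.4.3). Neither section mentions AEs.

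Safety of pembrolizumab after TMZ is a secondary objective for cohort P (5.2). Section 10.3.1 pools everyone who received either drug in one safety population, and section 10.3.3 reports AEs as proportions. Neither defines treatment-emergent events or assigns events to a drug.

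**The concern.** A site that works from the flow chart would conduct no formal AE review on the day pembrolizumab starts and would ask about AEs at no contact after about day 30. Two things are at stake, both for the secondary safety objectives.

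- Late serious immune events would be found only if a patient or another physician volunteers them, or if they surface incidentally at a visit held for another purpose. Section 9.2.3 does not oblige investigators to seek events actively in former participants.
- In cohort P, the safety of pembrolizumab after TMZ can be described only if toxicity carried over from TMZ is separated from toxicity that begins or worsens on pembrolizumab. Section 9.2.6 leaves out pre-existing conditions unless they worsen, but in cohort P the reporting period begins with TMZ. The reference state is therefore the one before TMZ, and no AE grade at the start of pembrolizumab is called for.

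**Working it through.** The plan gives no figure to reproduce. The check reads the chart row and then does day arithmetic on the stated windows.

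**Chart row.** The AE row has nine cells for nine columns. The alignment agrees with rows whose position is certain: pembrolizumab administration falls under its cycle 1 and cycle 2 onward, and survival status falls under survival follow-up. The blanks should still be confirmed on the typeset page.

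**After pembrolizumab**, counting all contacts from the end of treatment (an assumption):
- SAE window: 90 days. Last ticked AE review: about day 30. Days with no scheduled query: 90 − 30 = 60, and 60/90 = 67%.
- Follow-up visit, no progression: 56 ± 7 = day 49 to 63, inside the window. The next is at 2 × 56 = day 112, or 105 to 119, and could look back over day 90.
- Survival call, progression: 12 × 7 = day 84, also inside but 6 days short of day 90. The next is at day 168.
- If new anticancer therapy starts, 9.2.2 can end SAE reporting at day 30, so the gap largely closes for those patients.

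**Between TMZ and pembrolizumab (cohort P).** Assume TMZ is given on schedule and progression is found at the week-8 scan. The last dose is cycle 2 day 5, or 28 + 5 = day 33. The scan is 8 × 7 = day 56, which is 23 days later. If 9.2.2 is read as one window across both drugs, the gap is 0 days. If it is read per drug, with 30 days counted from the last TMZ dose, the gap depends on which limit on the start of pembrolizumab applies:

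| Limit on start | Latest start (day) | Days since last TMZ dose | Days beyond 30 |
|---|---|---|---|
| 28 days from the baseline scan, which is the TMZ progression scan (9.1.3.1) | 56 + 28 = 84 | 84 − 33 = 51 | 21 |
| 5 weeks from progression (7.6.1) | 56 + 35 = 91 | 91 − 33 = 58 | 28 |
| Week 5 counted from a biopsy taken 7 days after the scan (4.1.2; flow chart footnote 4) | 63 + 35 = 98 | 98 − 33 = 65 | 35 |

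If TMZ discontinuation is dated to the scan instead of the last dose, the same three limits give 0 days (28 is less than 30), 35 − 30 = 5 days and 42 − 30 = 12 days.

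Because 8 weeks is exactly two TMZ cycles, the 23 days recur at every scheduled scan when dosing is on time. A skipped cycle would lengthen the interval and a delayed one would shorten it.

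**Which reading of 9.2.2?** The AE sentence names either drug at the opening and study treatment as a whole at the close, which favours one window. The SAE sentence that follows speaks of a period for AEs of TMZ, which favours a window per drug. The text does not settle it.

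**The case against.** The strongest reply is that the text already covers most of this. SAEs to day 90 are required in two sections and ECIs in a third. Related SAEs are to be recorded "from the time a subject consents to participate in the study up to and including any follow-up contact", which would take in a serious complication of the post-TMZ biopsy. Follow-up visits include examination and concomitant-medication review, and section 7.6.1 ties medication recorded after day 30 to SAEs and ECIs. TMZ toxicity is reviewed at TMZ visits, dated (Table 9.2) and followed to resolution or stabilization (9.2.2). At pembrolizumab cycle 1 the chart ticks eligibility, examination, ECOG, ECG and laboratory tests, and exclusion 3 requires recovery from earlier toxicity to Grade 1 or baseline.

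All of that stands, and it rules out stronger readings that a reader might infer:

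- **That late serious events are excluded, or that no pre-dose baseline exists.** The duty to report is there and a partial baseline is there. What is missing is a scheduled query and a formal AE review.
- **That TMZ toxicity is first recorded at pembrolizumab cycle 2.** It should already be on the case report form with its dates.
- **That every cohort P patient has 35 uncollected days.** That figure needs the per-drug reading, the latest biopsy and the 5-week wording together. It passes over the 28-day imaging limit and describes a worst case, not each patient.
- **That all 54 treated patients have the late gap.** The 54 is a ceiling, since cohort D is up to 34 and cohort P can stop at 10, and patients who start new therapy largely leave the gap.
- **That an early safety visit shortens collection.** Section 9.1.7.4 says the visit "should be scheduled for a safety follow-up visit within 30 days after the last dose of study", and 9.1.7.4.1 says "All AEs that occur prior to the Safety Follow-Up Visit should be recorded". But 9.2.2 fixes AE collection to 30 days, and 9.2.6 requires follow-up for at least that long, whatever the visit date.

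The reply does not supply a contact that asks about AEs between day 31 and day 90, or a rule for dividing events between the two drugs.

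**Conclusion.** The flow chart and the text do not match, and the mismatch should be corrected. For patients who start no new anticancer therapy, 60 of the 90 days of the pembrolizumab SAE window have no scheduled AE query, even though an existing contact falls inside it. This assumes that contacts are counted from the end of treatment and that sites work from the chart.

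For cohort P the gap before pembrolizumab is uncertain: none if 9.2.2 means one window, and at most about 21 days if it means a window per drug, with progression at week 8, on-time dosing and the 28-day imaging limit. It reaches 28 to 35 days only under the looser 5-week wording. Those timing passages must be reconciled; this review does not say which should govern.

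The lack of a formal AE review at pembrolizumab start, and of a rule assigning events to the TMZ or pembrolizumab period, holds under either reading. The consequence is limited to the secondary safety objectives. The primary response-rate analysis is not affected.

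**What to change.** - In section 8.0, tick AE review before dosing at pembrolizumab cycle 1 for both cohorts.
- In section 9.2.2, state that AE collection is continuous from the first TMZ dose through pembrolizumab for patients who proceed.
- In sections 8.0, 9.1.7.4.2 and 9.1.7.4.3, add an SAE and ECI query to the existing follow-up visits and survival calls, with one contact at or after day 90 that looks back over the whole window.
- In section 10.3, count as pembrolizumab-emergent only events that are new, or worse in grade, compared with the cycle 1 pre-dose status, and report cohort P events separately for the TMZ and pembrolizumab periods.
- Reconcile the timing passages in 4.1.2, 7.6.1 and 9.1.3.1 so that the interval between TMZ and pembrolizumab is stated once.

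The cost is some extra case-report-form work and moving one survival call from about day 84 to day 90 or later. Patients without progression can be covered at the visit due around day 112. No new visit is needed.
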